**Test Product, Dose, and Mode of Administration:**

Bexagliflozin tablets, 20 mg or placebo, to be taken by mouth once daily in the morning

**Duration of Treatment:** up to 36 weeks

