### **9.7.1 Adverse Events**

AEs will be mapped to preferred term and body system using the Medical Dictionary for Regulatory Activities (MedDRA) dictionary. AEs that begin at or after the first administration of double-blind study medication (i.e., first dose of study 603A) or existing AEs that worsen in severity after the first dose of double-blind study medication are considered treatment emergent AEs (TEAE). Treatment emergent periods will be divided into three periods: study 603A, study 603B prior to randomization, and study 603B after randomization. The number and percentage of subjects reporting TEAEs will be summarized for each treatment group by MedDRA system organ class and preferred term, for each period as well as all periods combined. Further summaries by severity and by relationship to study treatment will also be provided. Drug-related AE will be considered those to be at least possibly related to the study treatments based on the investigators assessment.

Similarly, the number and percentage of subjects reporting serious AEs, and the number and percentage of subjects reporting AEs leading to treatment discontinuation will also be summarized for each treatment group by MedDRA system organ class and preferred term.

In addition, adverse events of special interest include, but not limited to UTI, GMI, hypoglycemia, hepatotoxicity, MACE, and DKA events, will be separately summarized.

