6.2.3. Last Dose Date

The date of the last dose will be recorded in CRF at Day -1, cumulative weeks 12, 24, and 36. The last dose date for 603A will be the date recorded at week 12 and 603B will be the one recorded at 603B week 24. The date of the last dose in integrated analyses will be the latest last dose dates for any bexagliflozin kit dispensed.

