9.1. EXTENT OF EXPOSURE

Study drug exposure will include:

- Treatment duration by treatment group
- Total dose received by treatment group

Treatment duration (in weeks) is calculated as (the date of the last dose of study drug - the date of the first dose of study drug + 1) / 7 and rounded to 1 decimal place. Total dose consumed will be calculated as number of tablets dispensed on the first day after randomization - number of tablets returned on the last day of the period. If any of the bottles dispensed are not returned, it will not be possible to compute the total dose consumed. In this case, the number of tablets consumed will be considered as missing.

Exposure will be summarized for study 603A, 603B, and integrated.

Summary statistics for treatment duration (in weeks) and total dose consumed, as well as a frequency summary of treatment duration categories (e.g., < 1, 1 - < 3 weeks), will be provided.

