9.2. TREATMENT COMPLIANCE

Subjects will be provided with dosing instructions each time study medication is dispensed. Subjects will also be instructed to bring their medication with them to every visit. Treatment compliance will be summarized by treatment for 603A and 603B.

Compliance in studies 603A, 603B, and integrated will be calculated as follows:

- Percent compliance = (number of tablets consumed / number of tablets that should have been taken) x 100.
- Number of tablets consumed is computed as in Section 9.1.
- Number of tablets should have taken = number of exposure days.
- Number of exposure days = last dose date - first dose date + 1.

If any of the bottles dispensed are not returned, the number of tablets consumed and compliance will be considered as missing. Compliance will be summarized for each period by actual treatment for safety analysis set. A separate table for overall compliance will be presented without treatment arms. A frequency summary of compliance will also be presented with the following categories: < 75%, 75-<100%,

100-120%, and > 120%.

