9.3. ADVERSE EVENTS

Adverse events will be collected and recorded after a subject is enrolled in the study to the last scheduled contact. Any new serious adverse events (SAE) reported by the subject to the investigator that occur after the last scheduled contact, and are determined by the investigator to be reasonably associated with the use of the investigational product, will be included in the analysis.

For all AEs, preferred AE terms and system organ class (SOC) will be coded using terminology from the Medical Dictionary for Regulatory Activities (MedDRA), version 19.0 or above.

A treatment-emergent adverse event (TEAE) is defined as an AE that begins (or an existing condition that worsens) after the first administration of double-blind study medication in study 603A). TEAE will be summarized separately for periods: study 603A and study 603B after randomization, dependent upon in which period the event started. TEAE summary for all periods combined will include all bexagliflozin TEAEs started on or after the first dose of bexagliflozin and before the last dose of bexagliflozin.

Drug-related AEs will be considered those to be possibly, probably and definitely related to bexagliflozin administration based on the investigator's assessment.

Unless otherwise specified, AEs will be summarized by SOC and PT, with SOCs and PTs within SOCs presented in descending order of subject incidence.

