9.3.1. Derived Data

AE onset day is calculated as (date of AE start - date of first double-blind dose of each study + 1).

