9.3.2. Data Summarization

The AE summaries will include:

- An overall summary of the number and percentage of subjects reporting any TEAEs, serious TEAEs, treatment-related TEAEs, serious treatment-related TEAE, any TEAEs leading to treatment discontinuation, any TEAEs leading to subject withdrawal and TEAEs leading to death.
- TEAEs overall and by SOC and PT
- TEAEs by severity, overall and by SOC and PT

- Serious TEAEs, overall and by system organ class and preferred term
- TEAEs by relationship to study treatment, overall and by system organ class and preferred term
- TEAEs leading to treatment discontinuation, overall and by SOC and PT
- TEAEs leading to study withdrawal, overall and by SOC and PT
- Common TEAEs. Common TEAEs are as TEAEs that occur in > 5% of the subjects in either of the treatment groups.

Except for common TEAEs, each data summary will be presented for the 603A period, for the 603B period after randomization, and for the integrated bexagliflozin treatment periods. Common TEAEs will be presented for the integrated bexagliflozin treatment period. Tables for the 603A will be summarized by treatment received in 603A and overall. The summary table for the 603B period after randomization will contain 2 layers: 1) 603B treatment, and 2) split 603B treatment by 603A treatment groups. Tables for integrated bexagliflozin treatment periods will present number and percentage of subjects with event, and exposure adjusted AE rate (i.e. rate per 100 patient years of bexagliflozin). Events will be summarized according to the actual treatment when the event starts. The denominator for percentage calculations will be the total number of subjects who receive at least one dose of the specified treatment. All subjects should have received at least one dose of bexagliflozin unless they were withdrawn from study 603A.

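### The integrated bexagliflozin TEAE window closes before the last dose, so an AE that follows the final tablet leaves the integrated tables, and in the 603B run-in no general TEAE table catches it

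*SAP*

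**What the plan says.** **The window.** SAP 9.3 takes into the combined summary only bexagliflozin TEAEs that "started on or after the first dose of bexagliflozin and before the last dose of bexagliflozin". Under SAP 9.3.2 every AE summary has an integrated version, including TEAEs leading to discontinuation. Those tables also report an "exposure adjusted AE rate (i.e. rate per 100 patient years of bexagliflozin"), without defining the patient-years.

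**Dates.** Both ends of the comparison are calendar dates. SAP 6.2.3: "The date of the last dose in integrated analyses will be the latest last dose dates for any bexagliflozin kit dispensed". SAP 9.3.1: "AE onset day is calculated as (date of AE start - date of first double-blind dose of each study + 1"). The protocol synopsis has the tablet "to be taken by mouth once daily in the morning".

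**Exposure.** SAP 9.1 computes treatment duration from "the date of the last dose of study drug - the date of the first dose of study drug + 1", and SAP 9.2 has "Number of exposure days = last dose date - first dose date + 1". SAP 6.2.5 does the same by period. All three count the last-dose day.

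**Periods.** Protocol 9.7.1: "Treatment emergent periods will be divided into three periods: study 603A, study 603B prior to randomization, and study 603B after randomization". SAP 9.3 keeps the first and third. SAP 12 records that the run-in will have no AE summary of its own and that the integrated set serves instead. SAP 9.3.3 nevertheless calls for run-in tables of AEs of special interest, and SAP 9 names a run-in safety set that SAP 5 does not define under that name.

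**Late SAEs.** SAP 9.3 also says that related SAEs reported after the last scheduled contact enter the analysis.

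**The concern.** An AE that starts soon after the day's tablet and makes the subject stop has its onset on the last-dose day, after the last dose. The window excludes it, although SAP 9.3.2 attributes each event to the treatment the subject was on at onset, which that day is bexagliflozin. The loss is therefore selective: it falls on events that end treatment at once, and it reaches the integrated discontinuation table, where a reader would look for them.

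The run-in is the exposed segment. The integrated table was made the replacement for the run-in summary, so an event outside its window has no other general TEAE table to fall into.

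**Working it through.** The plan states no figure for this point. Steps 1 and 2 apply its wording; steps 3 and 4 give the size.

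**1. The rule around the last dose.** Let L be the date of the last bexagliflozin dose.

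| Onset | Rule read by date | Rule read by clock time | On or before date L |
|---|---|---|---|
| L − 1 | counted | counted | counted |
| L, before the tablet | not counted | counted | counted |
| L, after the tablet | not counted | not counted | counted |
| L + 1 or later | not counted | not counted | not counted |

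The third row is lost under either reading. The second depends on a choice the SAP does not state.

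**2. Where an excluded event still appears.**

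| Last bexagliflozin dose in | General TEAE table by SOC and PT | Elsewhere |
|---|---|---|
| 603A | 603A period table | listings |
| 603B run-in | none | listings (SAP 9.3.2); run-in table if of special interest (SAP 9.3.3); withdrawal reason (SAP 7.1) |
| 603B after randomization | post-randomization table | listings |

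The run-in row includes subjects re-randomized to placebo. They take a bexagliflozin tablet at Visit 8 and start placebo the next day, so L is the Visit 8 date. Protocol 7.8 places laboratory tests, ECG, physical examination and AE assessment at Visit 8. Read by date, any AE dated to that visit in these subjects drops out.

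**3. Effect on the integrated rate.** Inputs from Protocol 9.2: 680 randomized 1:1, 626 left at week 12, and 75% (510) at week 36. Week 24 is not given; I assume the midpoint, 568, with range 510 to 626, and equal loss by arm.

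- Exposed to bexagliflozin: 340 + 313 = 653.
- One day each: 653 / 365.25 = 1.8 patient-years.
- Exposure (mean at risk × 84 / 365.25): 603A 326.5 gives 75; run-in 597 gives 137; withdrawal period 269.5 gives 62. Total 274 (264 to 284).
- Largest mismatch: 1.8 / 274 = 0.65% (0.68% to 0.63%).

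This supposes that the patient-years follow SAP 9.1, which is an inference.

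**4. Number of AEs lost.** Early bexagliflozin stops:

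- 603A: 340 − 313 = 27.
- Run-in: 626 − 568 = 58 (0 to 116).
- Withdrawal period, active arm: 284 − 255 = 29 (58 to 0).
- Total: 114 (85 to 143).

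Assume that 10–30% of stops are for an AE, and that 10–30% of those AEs start on the last-dose day after the tablet. Neither figure is in the documents. The product is 0.01 to 0.09.

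- Overall: 85 × 0.01 = 0.9 to 143 × 0.09 = 12.9.
- Run-in: 0 to 116 × 0.09 = 10.4, before AEs of special interest are removed.

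Other assumptions give other counts. If 2–8% of the 653 stop for an AE, and 10–50% of those AEs start on or after the last-dose date, the range is 653 × 0.02 × 0.10 = 1.3 to 653 × 0.08 × 0.50 = 26.1.

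For the last-dose day of about 284 subjects re-randomized to placebo, if 20–40% have a TEAE per 84 days (assumed, evenly spread), 284 / 84 × 0.20 to 0.40 gives 0.7 to 1.4 TEAEs. Findings made at the visit itself could raise this.

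**The case against.** The best defence is that the wording is loose drafting. SAP 9.3.2 attributes events by treatment at onset, and SAP 12 speaks of AEs during bexagliflozin treatment; neither shuts out the last-dose day. Some upper limit is also needed, because two of the four sequences move to placebo. Both points stand as far as they go, and a deliberate exclusion is not shown. But SAP 9.3 states an explicit limit, and a programmer would follow it.

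A reader might infer more than the documents support:

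- *That run-in AEs of this kind reach no summary at all.* They do not support this. SAP 9.3.3 keeps run-in tables for a long list of special-interest events, many of them plausible reasons to stop this drug class, and SAP 7.1 summarizes reasons for early withdrawal, though not by event term.
- *That the comparison with placebo is biased.* The 603A and post-randomization tables assign events by period of onset with no last-dose limit, and integrated summaries default to a single total column (SAP 6.1).
- *That the integrated rate is materially wrong.* Step 3 shows that it is not.

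The run-in wording conflict is mild: SAP 12 can be read as covering general TEAEs and SAP 9.3.3 as a specific exception. The hazard ratio versus placebo in Protocol 2.4 and SAP 3.4 has no planned analysis, but SAP 3.4 goes on to list frequency and severity objectives that are planned. Both are matters of wording.

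**Conclusion.** The point holds in this form. The upper limit in SAP 9.3 is wrong as written: it conflicts with the attribution rule in SAP 9.3.2, with exposure formulas that count the last-dose day, and with the role SAP 12 gives the integrated table. An AE after the final tablet leaves all integrated TEAE tables. If the last bexagliflozin dose fell in the run-in, it also has no general TEAE table by SOC and PT.

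The rate effect is about 0.65% at most, given the inferred patient-years. The count of lost AEs is undetermined: about 1 to 13 overall and 0 to 10 in the run-in under the assumed proportions and the full range of early stops, so the run-in loss could be nil. Confidence is high on the wording and low on the count. The correction should be made because the loss is selective and the cure is one phrase.

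**What to change.** 1. In SAP 9.3, change the upper limit to *on or before the date of the last dose of bexagliflozin*, and state in SAP 9.3.2 that patient-years run between the same first and last dose dates. Placebo starts the day after Visit 8, so this moves no placebo-day event to bexagliflozin.
2. In SAP 9.3, name the table that counts related SAEs reported after the last scheduled contact. The integrated window cannot hold them, before or after change 1.
3. Minor reconciliations: in SAP 12, except AEs of special interest (section 9.3.3) from the run-in sentence; align the run-in safety set in SAP 9 with SAP 5; reword the hazard-ratio objective to the counts and rates actually planned, and record that in SAP 12.

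The cost is a few lines of SAP text, with no new data and no effect on efficacy analyses. One limit remains: AEs that start the day after the last dose, including overnight, stay outside the integrated table.

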9.3.1. Derived Data

AE onset day is calculated as (date of AE start - date of first double-blind dose of each study + 1).

9.3.2. Data Summarization

The AE summaries will include:

- An overall summary of the number and percentage of subjects reporting any TEAEs, serious TEAEs, treatment-related TEAEs, serious treatment-related TEAE, any TEAEs leading to treatment discontinuation, any TEAEs leading to subject withdrawal and TEAEs leading to death.
- TEAEs overall and by SOC and PT
- TEAEs by severity, overall and by SOC and PT

- Serious TEAEs, overall and by system organ class and preferred term
- TEAEs by relationship to study treatment, overall and by system organ class and preferred term
- TEAEs leading to treatment discontinuation, overall and by SOC and PT
- TEAEs leading to study withdrawal, overall and by SOC and PT
- Common TEAEs. Common TEAEs are as TEAEs that occur in > 5% of the subjects in either of the treatment groups.

Except for common TEAEs, each data summary will be presented for the 603A period, for the 603B period after randomization, and for the integrated bexagliflozin treatment periods. Common TEAEs will be presented for the integrated bexagliflozin treatment period. Tables for the 603A will be summarized by treatment received in 603A and overall. The summary table for the 603B period after randomization will contain 2 layers: 1) 603B treatment, and 2) split 603B treatment by 603A treatment groups. Tables for integrated bexagliflozin treatment periods will present number and percentage of subjects with event, and exposure adjusted AE rate (i.e. rate per 100 patient years of bexagliflozin). Events will be summarized according to the actual treatment when the event starts. The denominator for percentage calculations will be the total number of subjects who receive at least one dose of the specified treatment. All subjects should have received at least one dose of bexagliflozin unless they were withdrawn from study 603A.

All AE summary tables will be prepared by actual treatment arm for the safety analysis set. For summary tables, subjects having more than 1 event with the same PT in the period will be counted once for that term. Subjects having more than 1 event with the same SOC in the period will be counted once for each event and once for that SOC. For tabulations by severity, only a subject's most severe event within the category (e.g. overall, SOC, PT) in the period will be counted; similarly, for tabulations by relationship, only a subject's most related event within a category in the period will be counted. The denominator for percentages will be the number of subjects in the safety analysis set for the given treatment group.

Listings will be provided for all AEs and the following subsets:

- All TEAEs at least possibly related to bexagliflozin
- Serious AEs
- AEs leading to treatment discontinuation
- AEs with outcome of death.

Additional information will be collected in the event diabetic ketoacidosis (DKA) is

suspected or observed. These data will be listed.

9.3.3. AEs of Special Interest

AEs of special interest include, but are not limited to, diuretic effects, urinary tract infections (UTI), genital mycotic infections (GMI), hypoglycemia, hepatotoxicity, major adverse cardiovascular events (MACE), diabetic ketoacidosis (DKA), hypotension episodes, malignancies, fractures, renal failure events, hypersensitivity reactions, rash, pyelonephritis or urosepsis, and events may be associated with SGLT2 inhibition, including amputations, , and Fournier’s gangrene. These AEs of special interest, except for MACE, will be prospectively identified based on the MedDRA PTs in the AEs log by a medical expert prior to the data base lock and unblinding of the individual subject treatment assignment. The list of AEs of special interest will be confirmed in a peer review process. MACE and hypoglycemia events by severity will be summarized separately. All AEs of special interest will be presented for 603A, 603B run-in, 603B post-randomization, and all periods combined in the same format as in Section 9.3.2.

9.3.3.1. AE of Special Interest Identified by PTs

The number and percentage of subjects experiencing TEAEs of special interest will be summarized for each treatment group by type of event. The incidence rate of AE of special interest per 100 patient years will also be summarized. Each category of events will be displayed in a separate listing.

9.3.3.2. Hypoglycemic Events

Hypoglycemic event categories include:

Category	Description
Severe	Assistance required and blood glucose ≤ 70 mg/dL or no value available but responded to glucose treatment
Documented Symptomatic	Blood glucose ≤ 70 mg/dL and typical symptoms of hypoglycemia
Asymptomatic	Blood glucose ≤ 70 mg/dL and no typical symptoms of hypoglycemia
Probable Symptomatic	Typical symptoms of hypoglycemia and no value available but responded to glucose treatment
Relative	Typical symptoms of hypoglycemia and blood glucose > 70 mg/dL

While each event meeting the criteria above will be entered into the hypoglycemia log, only critical (severe) hypoglycemia, documented symptomatic hypoglycemia, asymptomatic hypoglycemia, and probable hypoglycemia will be entered as AEs.

The number and percentage will be summarized for the integrated bexagliflozin treatment period:

- Each category of hypoglycemic event;
- Any severe or documented hypoglycemic events.

9.3.3.3. Major Adverse Cardiovascular Events

Cardiovascular events considered to be potential MACE by the investigator will be submitted to an independent CEC for adjudication. The events of interest include cardiovascular mortality, MI, stroke, hospitalization for acute coronary syndromes, urgent revascularization procedures, and other possible serious cardiovascular events. The number, percentage and incidence rate per 100 patient years of adjudicated MACE will be summarized for each treatment group. Adjudicated MACE will be further summarized by PTs.

9.4. LABORATORY EVALUATIONS

Laboratory tests will include hematology panel, chemistry panel, serum lipids, and urinalysis testing. Hematology, HbA1c, chemistry, serum lipids, and urinalysis will be performed at the following time points: at the screening visit (Week - 12), on Day -1 visit, and at cumulative week 12, 24, and 36. A list of laboratory tests is included in Table 3.

Low density lipoprotein cholesterol (LDL-C) will be calculated by the Friedewald equation. If triglycerides are > 400 mg/dL, the calculated LDL-C value is invalid by this equation and will be set as missing. Direct LDL-C will be determined in subjects whose triglycerides are > 350 mg/dL at screening visit. All subsequent LDL-C of these subjects will be determined by the same direct LDL-C measurements only. If triglycerides are >350 mg/dL, a reflex test will be performed based on direct LDL measurement. The following algorithm will be used to obtain LDL-C values for the analyses:

1. Select subjects (based on the SI unit) who had screening triglycerides >3.4 or >350 based on the conventional unit
2. Take the LDL - direct measurement values only, throughout the study visits for those subjects
3. If screening triglycerides > 350 and no direct LDL-C values have been determined, take the calculated.

Among those subjects who have screening triglycerides >350 and have both calculated and direct LDL values, only the direct LDL will be analyzed.

Urinalysis microscopy will be conducted if the subject has a positive result on the leukocyte esterase or nitrite dipstick tests to clarify the significance of the finding. Results of glucose measurement in the urinalysis must be suppressed from the laboratory reports so the sponsor, investigators, study coordinators, pharmacists, study subjects, and the CEC members will remain blinded to the dosing assignment.

All scheduled and unscheduled results will be considered in tables that assess maximum severity.

Observed values (in SI units) and change from baseline over time will be summarized for each scheduled visit and the end of the study visit. Laboratory data will be classified as low, normal, or high relative to the parameter's reference range. Laboratory abnormalities for each treatment will also be summarized with shift tables for selected parameters. All summary tables will be presented by treatment group and for each visit for study 603A and 603B. In addition, summaries based on assessments from both studies (603A and 603B) will also be presented by weeks of exposure of bexagliflozin (12 weeks, 24 weeks, and 36 weeks).

All continuous variables will be summarized by number of subjects [n], mean, SD, Q1, median, Q3, minimum and maximum and categorical variables will be summarized by frequency and percentage. For hematology, chemistry, and serum lipids, columns will be included for normal ranges and individual abnormal laboratory values will be flagged and clinical significance will be indicated. A listing for the microscopic examination will be provided for subjects who have a positive result from the urinalysis dipstick evaluation.

Table 3 List of Laboratory Tests

Hematology:
 
 • Hematocrit (Hct) • Hemoglobin (Hgb) • Mean corpuscular hemoglobin (MCH) • Mean corpuscular hemoglobin concentration (MCHC) • Mean corpuscular volume (MCV) • Platelet count • Red blood cell (RBC) count • White blood cell (WBC) count with differential 
Urinalysis:
 
 • Appearance • Bilirubin • Color • Glucose • Ketones • Microscopic examination of sediment • Nitrite • pH • Protein • Specific gravity • Urobilinogen 
Pregnancy test: Urine human chorionic gonadotropin (hCG) (only for females who are not diagnosed as postmenopausal)
	
Serum Chemistry:
 
 • Albumin (ALB) • Alkaline phosphatase (ALK-P) • Alanine aminotransferase (ALT) • Aspartate aminotransferase (AST) • creatinine kinase (CK) • Blood urea nitrogen (BUN) • Calcium (Ca) • Bicarbonate (HCO₃) • Chloride (Cl) • Creatinine • Glucose • Magnesium (Mg) • Phosphorus • Potassium (K) • Sodium (Na) • Total bilirubin • Direct bilirubin • Total cholesterol • HDL-cholesterol • LDL-cholesterol • Total protein • Triglycerides • Uric acid 
Glycemic control
 
 • HbA1c 
Population PK Sampling
 
 • Bexagliflozin plasma level
--	--

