## 6.9.2 Sample Collection, Storage, and Shipping

### 6.9.2.1 Hematology, Blood Chemistry, Serum Lipids, and Glycemic Control Assessments

Blood samples for hematology, chemistry, serum lipids and glycemic control assessments shall be collected. Subjects shall be in a seated or supine position during blood collection. Samples shall be collected at the time points indicated in the schedule of events in [Appendix 1](#) and [Appendix 2](#).

The study staff shall contact each subject prior to a scheduled clinic visit to confirm the time of the visit and to remind the subject of proper fasting practice. A subject must be queried to assess compliance with approximately 8 h fast prior to blood draw to ensure the lipid values can be accurately determined. If a subject has not fasted, the subject should return as soon as can be arranged to provide a specimen after proper fasting.

LDL-C will be calculated by the Friedewald equation. If triglycerides are > 400 mg/dL, the calculated LDL-C value is invalid by this equation and will be set as missing. Direct LDL-C will be determined in subjects whose triglycerides are > 350 mg/dL at the screening visit. All subsequent LDL-C of these subjects will be determined by the same direct LDL-C measurements only.

An investigator can perform additional laboratory testing to diagnose or to follow up an adverse event progression or resolution. Clinical samples should be analyzed in a local laboratory if a fast turnaround is necessary to determine the treatment plan.

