3.7. DETERMINATION OF SAMPLE SIZE

The primary efficacy endpoint of study 603A is the change from baseline (Day 1) to week 12 in the 24-hour average SBP of the bexagliflozin group compared to the placebo group using superiority testing at an overall two-sided 0.05 level of significance.

The primary efficacy endpoint of study 603B is the change from week 12 to week 24 in the 24-hour average SBP in the bexagliflozin group compared to the placebo group using superiority testing at an overall two-sided 0.05 level of significance.

Although the patient population was anticipated to be nearly identical between the two studies, they were to be carried out as independent investigations with respect to their individual primary and secondary endpoints. The assumptions used to estimate the sample size for the primary endpoint of study 603A were:

1. The magnitude of the decrease from baseline (Day 1) to week 12 of the 24 h mean SBP in the bexagliflozin treatment arm will exceed that found in the placebo arm by 5 mm Hg;
2. The standard deviation of the change from baseline to week 12 will be 15 mm Hg for both the active and placebo groups;
3. The two-sided significance level is 0.05.

The assumptions to estimate the sample size required for the primary endpoint of study 603B were:

1. Bexagliflozin will remain effective for at least 24 weeks. The 24-hour average ABPM SBP will not change between Week 12 and Week 24.
2. Subjects who are randomized to receive placebo will show an increase in ABPM SBP of 4 mm Hg between Week 12 and Week 24.
3. The standard deviation of the change is 15 mm Hg for both the active and placebo groups.
4. The two-sided significance level is 0.05.

A sample size of 254 per arm is required for the measurement to have 85% power to attain significance for the second primary endpoint. It is estimated that 75% of subjects will have completed the 36 weeks of study treatment since the first randomization. Thus a total sample size of 680 subjects is planned for the first randomization. It is estimated that approximately 8% will drop out for the first 12 weeks. A sample size of 626 subjects at the end of the first 12 weeks will provide >95% power for the first primary endpoint.

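### SAP 9.4 pairs >3.4 (SI) with >350 mg/dL as one triglyceride cut-off, but 350 mg/dL is about 3.95 mmol/L, so valid calculated LDL-C may be dropped at about 301-350 mg/dL

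*SAP*

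**What the plan says.** Protocol 6.9.2.1 sets the trigger for direct measurement: "Direct LDL-C will be determined in subjects whose triglycerides are > 350 mg/dL at the screening visit". SAP 9.4 repeats it ("Direct LDL-C will be determined in subjects whose triglycerides are > 350 mg/dL at screening visit") and adds a reflex rule at the same level: "If triglycerides are >350 mg/dL, a reflex test will be performed based on direct LDL measurement". Both documents void the Friedewald-calculated LDL-C only when triglycerides exceed 400 mg/dL.

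SAP 9.4 then gives a three-step algorithm for choosing the LDL-C values to analyze:

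- Step 1: "Select subjects (based on the SI unit) who had screening triglycerides >3.4 or >350 based on the conventional unit".
- Step 2: "Take the LDL - direct measurement values only, throughout the study visits for those subjects".
- Step 3: "If screening triglycerides > 350 and no direct LDL-C values have been determined, take the calculated".

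A closing sentence says that direct values take precedence when a subject above 350 at screening has both kinds. Neither step 3 nor that sentence prints a unit or an SI value. Later in the same section, the laboratory summaries are specified in SI units: "Observed values (in SI units) and change from baseline over time will be summarized".

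**The concern.** Step 1 treats 3.4 in SI units and 350 in conventional units as two forms of one cut-off. If they differ, step 1 selects a different set of subjects depending on the unit used, while step 3 is written only in terms of 350. Subjects between the two thresholds could then be caught by the direct-only rule in step 2 without having direct measurements and without qualifying for the fallback.

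At stake is whether SAP 9.4 defines one LDL-C data set. Under some codings, a group defined by raised screening triglycerides would drop out of the by-visit LDL-C summaries and of the integrated summaries at 12, 24 and 36 weeks of bexagliflozin exposure, although usable values exist.

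**Working it through.** **Inputs**

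- From SAP 9.4: step 1 cut-offs of 3.4 (SI, taken as mmol/L) and 350 (conventional, mg/dL); step 3 cut-off of 350; calculated LDL-C void above 400 mg/dL.
- From protocol 6.9.2.1 and SAP 9.4: direct LDL-C trigger above 350 mg/dL at screening.
- Assumption, not in the documents: 88.57 mg/dL of triglyceride per mmol/L, range 87.5-89.0.

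**1. Can the plan's figure be reproduced?**

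mmol/L = (mg/dL) / factor

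- 350 / 88.57 = 3.95 mmol/L (350 / 89.0 = 3.93; 350 / 87.5 = 4.00).
- Reverse: 3.4 × 88.57 = 301 mg/dL (3.4 × 87.5 = 297.5; 3.4 × 89.0 = 302.6).
- The SI cut-off is too low by (3.95 − 3.4) / 3.95 = 13.9%.

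The figure 3.4 is not reproduced. A wider range of 85-90 mg/dL per mmol/L (mean molar mass 850-900 g/mol) gives 3.89-4.12 mmol/L for 350 mg/dL, and 289-306 mg/dL for 3.4 mmol/L. A match would need 350 / 3.4 = 102.9 mg/dL per mmol/L, a molar mass of about 1029 g/mol. Expressing 350 mg/dL as 3.5 g/L, or using the cholesterol factor (9.05 mmol/L), does not give 3.4 either. Reading 3.4 as rounded from 3.35-3.45 gives 297-306 mg/dL, still well short of 350.

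**2. Who falls between the two thresholds?**

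Subjects with screening triglycerides of about 301-350 mg/dL (3.40-3.95 mmol/L). The validity limit for calculated LDL-C, 400 mg/dL, is 400 / 88.57 = 4.52 mmol/L, so at screening the whole band lies below it.

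**3. What does the algorithm do with them?**

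Test values were 310, 325 and 345 mg/dL (3.50, 3.67 and 3.90 mmol/L). All three behave alike:

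| Step 1 coded as | Step 3 coded as >350 mg/dL | Step 3 coded as >3.4 mmol/L |
|---|---|---|
| >3.4 mmol/L | selected, no fallback: calculated value dropped | selected, fallback applies: kept |
| either condition (union) | selected, no fallback: calculated value dropped | selected, fallback applies: kept |
| >350 mg/dL only | not selected: kept | not selected: kept |

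Two of these six combinations drop the values and four keep them. In the two that drop them, step 2 demands direct LDL-C, but the screening trigger is above 350 mg/dL. A direct value would exist only if triglycerides later exceeded 350 mg/dL and the reflex test was run.

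**4. How many values per affected subject?**

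Lipids are drawn at screening, Day -1 and cumulative weeks 12, 24 and 36 (Protocol Appendix 2; SAP Table 1). SAP 3.7 assumes about 8% dropout by week 12, so 92% remain, and for week 36: "It is estimated that 75% of subjects will have completed the 36 weeks of study treatment since the first randomization". Week 24 retention is not stated and must lie between the two.

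Expected post-baseline draws = 0.92 + (0.75 to 0.92) + 0.75 = 2.42 to 2.59 of 3.

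The baseline value is also at risk. Any visit with a reflex direct test is not. This counts scheduled blood draws, not cells in the summary tables.

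**The case against.** The strongest reply is that the intended rule is obvious. Every other statement of the threshold, in both documents, is 350, so 3.4 looks like a conversion slip that program quality control (SAP 14) may catch. Data are lost only if steps 1 and 3 are coded in different units. A programmer working wholly in SI would need an SI value for step 3, would find only 3.4, and would keep the calculated values. The six combinations are not equally likely and need not be exhaustive. LDL-C is a descriptive safety variable, one of many serum chemistry analytes, with no hypothesis test.

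Much of this stands. The loss is conditional, the count of codings is not a probability, and the stakes are small. The draw count is also not a count of contributions to the tables: week 24 serves as baseline for the randomized part of 603B, and the integrated tables run by weeks of exposure, so the time points per subject depend on treatment sequence.

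The reply does not remove the error. The wrong number sits in an operative selection rule. Both codings that lose data follow readily from the text: step 1 names the SI unit first and joins the conditions with 'or', and step 3's unlabeled 350 makes sense only in mg/dL. SAP 12 lists no intended change to the cut-off. A check of the program against the SAP could pass, because the program would match what is printed.

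**Conclusion.** The point holds. The SI cut-off in step 1 is not 350 mg/dL under any plausible conversion factor. It corresponds to about 301 mg/dL (298-303 over the assumed range; 289-306 over the wider one). The mismatch is certain, while the loss of data depends on how steps 1 and 3 are coded.

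Where it occurs, subjects with screening triglycerides of about 301-350 mg/dL lose calculated LDL-C that the SAP regards as valid, on average 2.4-2.6 of three scheduled post-baseline draws plus baseline, less any visit with a reflex direct test. The number of such subjects cannot be derived from the documents. No efficacy endpoint is affected. Selection uses a pre-randomization value, so no imbalance between the 603A arms is claimed. This should be corrected, but it does not threaten the trial's main conclusions.

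**What to change.** In SAP 9.4 step 1, replace the SI value with >3.95 mmol/L (350 mg/dL). Print the same cut-off with units in step 3 and in the sentence that follows it, so that every step matches the direct LDL-C trigger in SAP 9.4 and protocol 6.9.2.1. Because 3.95 rests on the assumed factor, treat 350 mg/dL as the governing value and confirm the SI figure against the central laboratory's own conversion.

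The cost is one number and two unit labels in the SAP, and one constant in the program. No added data or analysis is needed.
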